16.7 Early Safety Analysis

An early safety analysis will be performed after 6 patients have been accrued to each arm of the study and observed for one cycle. Accrual will be temporarily halted while these patients are evaluated. If 2 or more of the first 6 patients experience a DLT, as defined below, then the dose level will be reduced as defined in Section 8.0 and another six patients will be treated. If $< 2/6$ patients experience toxicities defined as DLT, then this dose level will be defined as the operational MTD and moved into the expansion portion. Further dose de-escalation to dose level -2 will follow the same guidelines.

Should additional modification be necessary, the study will be closed and evaluated by the study team regarding continuation. Upon determination of the safe dose level, the study will re-open for accrual.

16.8 Ongoing Safety Analysis

Ongoing safety monitoring will occur continuously; patient-level unacceptable toxicity will be defined as per DLT criteria (Section 7.4) and we will require a toxicity rate of no more than 20%. Monitoring for toxicity will follow a Bayesian-based rule for the probability that the unacceptable toxicity rate exceeds a maximal tolerated level of 20%. We will use a flat Beta(1,1) prior. Early termination for toxicity will be based on a posterior probability above 80% (in parentheses) that the toxicity rate exceeds 20%. Termination will be considered if DLT occurs in: 2 of 6 patients (0.85), 3 of 9 patients (0.88), 4 of 12 patients (0.90), 5 of 15 patients (0.92), 6 of 18 patients (0.93), or 6 of 21 patients (0.87).

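### Section 16.8 lists 6 of 18 DLTs as the toxicity boundary, but 5 of 18 already exceeds the section's own 80% posterior cut-off (0.84)

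*Combined protocol and SAP*

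**What the plan says.** Everything needed is in section 16.8, Ongoing Safety Analysis.

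- Prior: "We will use a flat Beta(1,1) prior".
- Quantity monitored: "the probability that the unacceptable toxicity rate exceeds a maximal tolerated level of 20" per cent.
- Rule: "Early termination for toxicity will be based on a posterior probability above 80% (in parentheses) that the toxicity rate exceeds 20" per cent.
- Boundary list, first half: "Termination will be considered if DLT occurs in: 2 of 6 patients (0.85), 3 of 9 patients (0.88), 4 of 12 patients (0.90").
- Boundary list, second half: "5 of 15 patients (0.92), 6 of 18 patients (0.93), or 6 of 21 patients (0.87").
- Frequency: "Ongoing safety monitoring will occur continuously".

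The case of 5 DLTs in 18 patients is not listed, and no other section gives a different boundary for n = 18.

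**The concern.** The list should turn the 80% rule into counts, so each entry should be the smallest number of DLTs whose posterior exceeds 0.80 at that sample size. The required count rises by one at every step from n = 6 to n = 18 and then stays at 6 from n = 18 to n = 21. The printed posterior climbs to 0.93 and drops back to 0.87. That pattern suggests that the n = 18 count is one too high.

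This is a safety boundary, and the study team and the DSMC are more likely to read the printed counts than to recompute a Beta tail. If the entry is one DLT too high, the same paragraph gives two answers for an arm at 5 of 18: the rule says the excess-toxicity criterion is met, and the list says nothing.

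**Working it through.** **Inputs (all section 16.8).** Prior Beta(1,1), toxicity limit 0.20, posterior cut-off above 0.80, looks at n = 6, 9, 12, 15, 18 and 21.

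**Formula.** With x DLTs in n patients the posterior is Beta(1 + x, 1 + n − x). For these integer parameters,

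P(rate > 0.20 | x, n) = P(Y ≤ x), where Y ~ Binomial(n + 1, 0.20).

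**Step 1: reproduce the plan's figures, then try one DLT fewer.**

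| n | Listed count | Printed | Recomputed | One DLT fewer | Posterior |
|---|---|---|---|---|---|
| 6 | 2 | 0.85 | 0.852 | 1 | 0.577 |
| 9 | 3 | 0.88 | 0.879 | 2 | 0.678 |
| 12 | 4 | 0.90 | 0.901 | 3 | 0.747 |
| 15 | 5 | 0.92 | 0.918 | 4 | 0.798 |
| 18 | 6 | 0.93 | 0.932 | **5** | **0.837** |
| 21 | 6 | 0.87 | 0.867 | 5 | 0.733 |

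The six printed values match, so the prior and the method are not in doubt. In five rows the next lower count falls below 0.80. At n = 18 it does not.

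**Step 2: the n = 18 row in full.** For 5 of 18 the posterior is Beta(6, 14), and with Y ~ Binomial(19, 0.20):

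P(Y ≤ 5) = 0.0144 + 0.0685 + 0.1540 + 0.2182 + 0.2182 + 0.1636 = 0.8369.

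For 4 of 18 the sum stops one term earlier, at 0.673. The minimum count is therefore 5.

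**Step 3: can 5 of 18 occur?** Yes. Four DLTs in 15 (0.798) does not trigger the rule, and one more DLT in the next three patients gives 5 of 18.

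**Step 4: could another cut-off or prior explain the list?** A higher cut-off would have to exclude 0.837 (5 of 18) and keep 0.852 (2 of 6), while the text states 80%. Under a Beta(0.5, 0.5) prior, 5 of 18 still gives 0.801, and the printed posteriors fit Beta(1,1).

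**Step 5: size.** The probability of reaching the boundary was computed by exact recursion for one arm, treating each boundary crossing as a stop. Each cell shows the list as printed → with 5 at n = 18.

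| True DLT rate | At the n = 18 look | At the n = 21 look | Any look to n = 18 | Any look to n = 21 |
|---|---|---|---|---|
| 20% | 0.008 → 0.047 | 0.032 → 0.013 | 0.428 → 0.467 | 0.460 → 0.480 |
| 30% | 0.018 → 0.071 | 0.055 → 0.021 | 0.729 → 0.782 | 0.784 → 0.803 |
| 35% | 0.019 → 0.063 | 0.049 → 0.018 | 0.838 → 0.882 | 0.887 → 0.899 |

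At a true rate of 10% the total to n = 21 goes from 0.132 to 0.136; at 40% it goes from 0.949 to 0.955.

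**The case against.** Several points can fairly be made for the plan as written.

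- **The printed entry is not a false statement.** 6 of 18 does give 0.93, which exceeds 0.80. The defect is that 5 of 18 also qualifies and is left out. This is right, and it describes the error more exactly, but the rule and the list still disagree.
- **The rule may govern, not the list.** A team that applies the 80% sentence directly would flag 5 of 18. In that case the list is wrong and should be corrected.
- **Termination is only to be considered.** Crossing the boundary prompts a decision and does not stop the arm automatically, and section 20.0 adds DSMC and medical-monitor review. The list nevertheless triggers that consideration, and it misses a case that meets the criterion.
- **The net effect is small.** This stands. At a true rate of 30%, the gain of 5.3 percentage points at n = 18 is mostly earlier detection: 3.5 points come from the n = 21 look and only 1.8 are new. With maximum accrual of 23, 22 and 22 (sections 16.22 and 16.23), stopping at 18 spares at most 4 or 5 patients per arm.
- **The totals are not the trial's true operating characteristics.** This also stands. They count 2 of 6 as a stop (0.580 of the 0.784 at 30%), whereas section 16.7 responds to 2 or more of 6 with a lower dose level and another six patients. The comparison between the two lists is informative; the absolute totals should be read with that in mind.

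**Conclusion.** The concern holds. Under the prior, limit and cut-off stated in section 16.8, the n = 18 entry is one DLT too high, and it is the only listed entry that is not the minimum qualifying count.

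The consequence is modest. It adds at most about 2 percentage points to the overall probability of reaching the boundary over six looks, for true rates of 10% to 40%. The gain is about 4 to 5 points at true rates of 20% to 35% where n = 18 is the last listed look reached. That may apply in Arms B and C, which are sized at 20 evaluable patients each. The direction is unfavourable, because an arm that meets the plan's own criterion for excess toxicity is not flagged.

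The posterior result rests only on the figures in section 16.8. The stopping probabilities also assume independent patients with a constant DLT rate, looks only at the six listed sample sizes, and a stop at every crossing.

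**What to change.** Make the n = 18 entry agree with the stated rule: replace 6 of 18 (0.93) with 5 of 18 (0.84). If the sponsor intended a different boundary at that look, section 16.8 should state the criterion that produces it. The cost is one number in the text and about 2 percentage points more chance of prompting a termination decision in an arm followed to n = 21.

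A separate and optional clarification: monitoring is described as continuous, but counts are given only at multiples of three. The section could say whether the rule applies only at the listed sample sizes or after every patient. If the latter, the minimum counts in between should be printed, for example 3 of 10 (0.839), 4 of 14 (0.836) and 5 of 19 (0.804). This costs more than the one-number correction. Looking after every patient from n = 6 to n = 21 raises the probability of reaching the boundary from 0.460 to 0.517 at a true rate of 20%, and from 0.784 to 0.829 at 30%, relative to the list as printed.

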16.9 Inclusion of Women and Minorities

16.91 This study will be available to all eligible patients, regardless of race, gender, or ethnic origin.

16.92 There is no information currently available regarding differential effects of this regimen in subsets defined by race, gender, or ethnicity, and there is no reason to expect such differences to exist. Therefore, although the planned analysis will, as always, look for differences in treatment effect based on racial and gender groupings, the sample size is not increased in order to provide additional power for subset analyses.

17.0 Source Documents and Access to Source Data

Source data is all information, original records of clinical findings, observations, or other activities in a clinical trial necessary for the reconstruction and evaluation of the trial. Source data are contained in source documents. Source documentation refers to original records of observations, clinical findings, and evaluations that are subsequently recorded as data. All entries should be printed legibly in black ink. If any entry error has been made, to correct such an error, draw a single straight line through the incorrect entry and enter the correct data above it. All such changes must be initialed and dated. DO NOT ERASE OR WHITE OUT ERRORS. For clarification of illegible or uncertain entries, print the clarification above the item, then initial and date it.

TrialMaster, an electronic database capture system will be created to record the data for this trial. Research coordinators will input clinical trial data into the database. This database is password protected and only the PI, assigned study team members, and CTO staff will have access to the database. DataCore, a core resource of the institution, will provide the primary data collection instrument for the study. All data requested in the system must be reported. All missing data must be explained. The quality assurance specialists will monitor this trial every 4-6 weeks for data entry accuracy.

Source documentation should be consistent with data entered into any electronic medical record or the electronic data capture system. Relevant source documentation to be reviewed by the DSMC throughout the study includes:

1. Baseline measures to assess pre-protocol disease status
2. Treatment records
3. Adverse events

Access to study records will be limited to IRB-approved members of the study team. The investigator will permit study-related monitoring, audits, and inspections by the CTO, IRB/EC, the sponsor, government regulatory bodies, and University compliance and quality assurance groups of all study related documents (e.g. source documents, regulatory documents, data collection instruments, study data etc.). The investigator will ensure the capability for inspections of applicable study-related facilities (e.g. pharmacy, diagnostic laboratory, etc.).

Participation as an investigator in this study implies acceptance of potential inspection by government regulatory authorities and applicable University compliance and quality assurance offices.

18.0 Ethics/Protection of Human Subjects

18.1 Ethical Standard

The investigator will ensure that this study is conducted in full conformity with Regulations for the Protection of Human Subjects of Research codified in 45 CFR Part 46, 21 CFR Part 50, 21 CFR Part 56, and/or the ICH E6.

18.2 Institutional Review Board

The protocol, informed consent form(s), recruitment materials, and all participant materials will be submitted to the IRB for review and approval. Approval of both the protocol and the consent form must be obtained before any participant is enrolled. Any amendment to the protocol will require review and approval by the IRB before the changes are implemented to the study. All changes to the consent form will be IRB approved; a determination will be made regarding whether previously consented participants need to be re-consented.

18.3 Informed Consent Process

18.31 Consent/Assent and Other Informational Documents Provided to Participants

Consent forms describing in detail the study agent, study procedures, and risks are given to the participant and written documentation of informed consent is required prior to starting intervention/administering study product.

18.32 Consent Procedures and Documentation

The consenting process and documentation will follow Standard Operating Procedures (Obtaining Informed Consent for Clinical Trials) of the NYU Langone Health PCC CTO.

18.33 Informed Consent

A participating investigator who has completed requisite training for human subject research and has been instructed by the Principal Investigator about the potential participant; also must address any questions/concerns prior to obtaining written informed consent for participation and HIPAA authorization can also obtain consent.

Patients will be given adequate time to read the consent form. They will be given time to ask questions about the study in private exam rooms. Questions will be answered by a participating physician, or qualified research study team member all of whom have completed requisite training for human subject research. Investigators will review the informed consent form with patients and address any questions or concerns prior to obtaining written informed consent for participation. Investigators will stress that participation in the study is completely voluntary and will not affect the care patients receive or result in any loss of benefits to which patients are otherwise entitled.

The Investigator will explain to each potential participant the nature of the study, its purpose, the procedures involved, the expected duration, the potential risks and benefits involved, potential compensation and or costs incurred by the patient and any discomfort this trial may entail. This informed consent should be given by means of standard written statement, written in non-technical language. All patients will be required to sign a written informed consent prior to being registered on this study. No patient can enter the study before his/her informed consent has been obtained. Every effort will be made to answer questions raised by patients and their families or advocates regarding the protocol and alternative therapies prior to asking a patient to sign the consent form.

The informed consent form is considered to be part of the protocol, and must be submitted by the investigator with it for IRB approval.

If applicable

For non-English speaking patients, institutional translation services will be utilized. All procedures for consenting non-English speaking patients will be in accordance with NYU Langone Health PCC CTO guidelines and policies.

For patients who cannot read. A witness, not related to the research study will be present. The consent will be read to the patient. The patient will also be allowed to ask any questions s/he may have. The

investigator will ask the patient questions to ensure s/he understands the study. If the investigator determines the subject understands the study, the patient will mark an X where his/her name would go and the witness will sign the consent form.

18.34 Documentation of Consent

The Principal Investigator or IRB approved sub-investigator will be responsible for documentation in the medical record that consent has been obtained from all participants. A signed copy of the consent form will be given to each participant. Original consent forms will be stored in the subject's medical chart.

18.4 Participant and Data Confidentiality

Information about study subjects will be kept confidential and managed according to the requirements of the Health Insurance Portability and Accountability Act of 1996 (HIPAA). Those regulations require a signed subject authorization informing the subject of the following:

- What protected health information (PHI) will be collected from subjects in this study
- Who will have access to that information and why
- Who will use or disclose that information
- The rights of a research subject to revoke their authorization for use of their PHI.

In the event that a subject revokes authorization to collect or use PHI, the investigator, by regulation, retains the ability to use all information collected prior to the revocation of subject authorization. For subjects that have revoked authorization to collect or use PHI, attempts should be made to obtain permission to collect at least vital status (i.e. that the subject is alive) at the end of their scheduled study period.

Participant confidentiality is strictly held in trust by the participating investigators, their staff, and the sponsor(s) and their agents. This confidentiality is extended to cover testing of biological samples and genetic tests in addition to the clinical information relating to participants. Therefore, the study protocol, documentation, data, and all other information generated will be held in strict confidence. No information concerning the study or the data will be released to any unauthorized third party without prior written approval of the sponsor.

The study monitor, other authorized representatives of the sponsor, representatives of the IRB or pharmaceutical company supplying study product may inspect all documents and records required to be maintained by the investigator, including but not limited to, medical records (office, clinic, or hospital) and pharmacy records for the participants in this study. The clinical study site will permit access to such records.

The study participant's contact information will be securely stored at each clinical site for internal use during the study. At the end of the study, all records will continue to be kept in a secure location for as long a period as dictated by local IRB and Institutional regulations.

Study participant research data, which is for purposes of statistical analysis and scientific reporting, will be transmitted to and stored at NYU Langone Medical Center. This will not include the participant's contact or identifying information. Rather, individual participants and their research data will be identified by a unique study identification number. The study data entry and study management systems

used by clinical sites and by NYU Langone Medical Center research staff will be secured and password protected. At the end of the study, all study databases will be de-identified and archived at the NYU Langone Medical Center.

18.41 Research Use of Stored Human Samples, Specimens, or Data

- Intended Use: Samples and data collected under this protocol may be used to evaluate the clinical efficacy of AZD1775 in combination with AraC in patients with newly diagnosed AML, relapsed/refractory AML, and hypomethylating agent failure MDS by performing state of the art molecular biomarker analysis. No hereditary genetic testing will be performed.
- Storage: Access to stored samples will be limited to the study team. Samples and data will be stored using codes assigned by the investigators. Data will be kept in password-protected computers. Only investigators will have access to the samples and data.
- Tracking: Data will be tracked using Trialmaster.
 - Disposition at the completion of the study: All stored samples will be sent to CBRD. Study participants who request destruction of samples will be notified of compliance with such request and all supporting details will be maintained for tracking.

Future Use of Stored Specimens

Data collected for this study will be analyzed and stored at the NYU Langone Health. After the study is completed, the de-identified, archived data will be transmitted to and stored via an electronic database system, under the supervision of [name], with the potential for use by other researchers including those outside of the study. Permission of storage of samples, specimens, and data are required to participate in this study and will be included in the informed consent.

With the participant's approval and as approved by local IRs, de-identified biological samples will be stored at the NYU Center for Biospecimen Research & Development. These samples could be used for research into the most appropriate treatment combinations for individuals with MPM and Hodgkin Lymphoma. The stored specimen and data will be coded and de-identified; the linking key will be maintained by the Principal Investigator. The CBRD will also be provided with a code-link that will allow linking the biological specimens with the phenotypic data from each participant, maintaining the masking of the identity of the participant.

During the conduct of the study, an individual participant can choose to withdraw consent to have biological specimens stored for future research. However, withdrawal of consent with regard to biosample storage will not be possible after the study is completed.

When the study is completed, access to study data and/or samples will be provided through the supervision of the principal investigator, [name], these sample will be stored indefinitely.

19.0 Data Handling and Record Keeping

19.1 Data Collection and Management Responsibilities

NYU's Datacore will be responsible for the development of a relevant database and data transfer mechanisms, along with appropriate validation of data and resolution of queries. Data generated within this clinical study will be handled according to the relevant standard operating procedures of the Clinical Trials Office at NYU.

Data collection is the responsibility of the clinical trial staff at the site under the supervision of the site PI. The investigator is responsible for ensuring the accuracy, completeness, legibility, and timeliness of the data reported.

All source documents should be completed in a neat, legible manner to ensure accurate interpretation of data. Black ink is required to ensure clarity of reproduced copies. When making changes or corrections, cross out the original entry with a single line, and initial and date the change. **DO NOT ERASE, OVERWRITE, OR USE CORRECTION FLUID OR TAPE ON THE ORIGINAL.**

Copies of the electronic CRF (eCRF) will be provided for use as source documents and maintained for recording data for each participant enrolled in the study. Data reported in the eCRF derived from source documents should be consistent with the source documents or the discrepancies should be explained and captured in a progress note and maintained in the participant's official electronic study record.

Clinical data (including AEs, concomitant medications, and expected adverse reactions data) and clinical laboratory data will be entered into Trialmaster, a 21 CFR Part 11-compliant data capture system provided by Omnicom. The data system includes password protection and internal quality checks, such as automatic range checks, to identify data that appear inconsistent, incomplete, or inaccurate. Clinical data will be entered directly from the source documents.

20.0 Quality Assurance and Quality Control

It is the responsibility of the Principal Investigator to oversee the safety of the study at his/her site. This safety monitoring will include careful assessment and appropriate reporting of adverse events as noted above, as well as the construction and implementation of a site data and safety-monitoring plan detailed below. Serious adverse events are evaluated regularly by the principal investigator in conjunction with the research team, the DSMC is notified of serious adverse events via email initially, reviewed offline by the designated medical monitor, and presented at the next DSMC monthly meeting. The Data Safety and Monitoring Committee (DSMC) will review the study at least quarterly. Medical monitoring will include a regular assessment of the number and type of serious adverse events.

Data and Safety Monitoring Committee

This investigator-initiated study will be monitored by the Data Safety Monitoring Committee (DSMC) of the New York University (NYU) Perlmutter Cancer Center (PCC). The DSMC operates based on the National Cancer Institute approved Charter. It is an existing and multidisciplinary committee (consisting of clinical investigators/oncologists, biostatisticians, nurses, and research administration staff knowledgeable of research methodology and design and in proper conduct of clinical trials) that is responsible for monitoring safety, conduct and

compliance in accordance with protocol data monitoring plans for interventional clinical trials conducted in the NYU Langone Health Perlmutter Cancer Center that are not monitored by another institution or agency. The DSMC reports to the Director of the NYU Langone Health PCC.

Per the NYU PCC Institutional Data Safety and Monitoring Plan, this phase II trial will be monitored by DSMC *quarterly* (from the date the first patient is enrolled), at protocol-specified interim time points, and at the completion of the study prior to study closure. This review includes accrual data, subject demographics and adverse events. Principal Investigators are required to attend the review of their studies. Additional reviews can be scheduled based on SAE reports, investigator identified issues, external information, etc. The DSMC will review safety data every 3 months.

